Epilepsy surgery involves resecting epileptogenic tissues including limbic structures which may be functionally normal. Hence the emergence process can be complicated in patients having diseased limbic structures or those having therapeutic removal of limbic structures as in epilepsy surgery. Limbic structures are responsible for memory, language and executive function and hence loss of some of these higher functions is to be expected in the postoperative period. Preoperative neuropsychological assessments are often used to predict their risk for postoperative loss of higher functions and behavior changes. In our experience the investigators have seen that there is a spectrum of emergence characteristics in patients undergoing temporal lobectomy that can vary from dangerously agitated patient to much sedated, unarousable patient. Delirium and agitation can be dangerous and have serious consequences for the patient such as injury, increased pain, hemorrhage, self-extubation and removal of catheters requiring physical or chemical restraint. On the other hand, the unarousable patient may pose dangerous airway complications and limit neurological assessment in the immediate postoperative period. Hence it is essential to have a clue about post anesthesia emergence behavior in patients having epilepsy

surgeries. The aim of this study is to look at the pattern of emergence from anesthesia after epilepsy surgery and to determine if preoperative neuropsychological assessment help predict the pattern of emergence in patients undergoing anterior temporal lobectomy and amygdalohippocampectomy.

Background

Emergence from anesthesia starts with activation of deep brain structures namely subcortical and limbic regions of the brain. Later they become functionally coupled with other parts of brain including frontal and inferior parietal cortex. Arousal (spoken command) induced brain activations during emergence from anesthesia are mostly localized in deep, phylogenetically old brain structures (limbic cortex or mesial temporal structures) than in neocortex.¹

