Physiologically, when emerging from deep anesthesia there will first be signs of autonomic arousal, followed by a slow return of brainstem reflexes, eventually leading to reflexive or uncoordinated movements that occur somewhat before subjects can willfully respond to simple commands. Thus, emergence of a conscious state, precedes the full recovery of neocortical processing required for establishing contact with the surroundings. The prevalence of epilepsy is around 0.4–0.8%² and 20–30% of these patients will develop medically refractory seizures²⁻⁴ and hence present for surgical treatment.

Epilepsy surgery involves resecting epileptogenic tissues including limbic structures which may be functionally normal. Anterior temporal lobectomy and amygdalohippocampectomy is a well-established surgical treatment for the patients with temporal lobe epilepsy and these parts of the brain have a role in the emergence from general anesthesia. Due to asymmetry of temporal neocortical (dominant vs nondominant) and mesial temporal functional representations, the loss of these structures and hence their functions in the postoperative period complicates emergence from anesthesia in these patients³. Preoperative neuropsychological assessments are often used to predict the risk for postoperative loss of higher functions and behavior changes.

Rationale

There are no study related interventions in this study and perioperative care of these patients will be as per our standard practice. The only study related protocol would be collecting the data on the emergence from anesthesia. The data will be collected from the time of turning off the anesthetic agents till the discharge from recovery room. Data collected include, vital signs, Glasgow coma scale (GCS), and Riker agitation- sedation score. The patients will be assessed every 5 minutes for the first 30 minutes and every 10 minutes for the next 60 minutes.

Study Objective and Hypothesis

The aim of this study was to look at the pattern of emergence from anesthesia after epilepsy surgery and to determine if preoperative neuropsychological assessment help predict the quality of emergence in patients undergoing anterior temporal lobectomy (ATL) and amygdalohippocampectomy (AH).

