We hypothesized that there will be a relationship between preoperative neuropsychological assessment scores and the limbic structure (hippocampus, amygdala and thalamus) volumes with the quality of emergence from anesthesia in patients undergoing anterior temporal lobectomy and amygdalohippocampectomy.

Study Design

This prospective, observational study will be conducted after approval from institutional ethics board and written informed consent will be obtained from each subject.

Eligibility Criteria

Inclusion Criteria:

- Adult patients above the age of 18 who are scheduled for elective anterior temporal lobectomy and amygdalohippocampectomy under General Anesthesia

Exclusion Criteria:

- Lack of informed consent
- Patients needing intensive care unit postoperatively

Study Procedure

Standard perioperative management

Anesthesia and neurosurgical care of the patients is as per the standard institutional practice. Preoperatively all patients will be seen by the anesthesiologists in the pre-anesthesia consult clinic.

Intraoperatively, all patients will have standard monitoring consisting of electrocardiography (ECG), pulse oximetry, end-tidal carbon dioxide (ETCO₂), invasive and non-invasive blood pressure, temperature, urine output, depth of anesthesia (Entropy) and end tidal anesthetic agent concentration.

Anesthesia induction will be with propofol (1-2 mg/kg), fentanyl (2-3mcg/kg) and rocuronium (0.8-1.2mg/kg).

Anesthesia will be maintained with oxygen, air, sevoflurane (0.8-1 MAC (Minimal Alveolar Concentration)) and remifentanyl infusion titrated to keep entropy within 45-55.

After induction and positioning, the surgery (ATL and/or AH) will be proceeded as per standard. After dural closure, inhalational agent concentration will be decreased gradually to MAC of 0.6 and fentanyl 1-2mcg/kg administered for additional analgesia.

After the closure of scalp, inhalational agent will be turned off.

Remifentanyl infusion will be turned off once the head is disengaged from head pins and after completion of the head dressing.

The patients will be allowed to wake up with “no touch technique”.

Extubation will be done when the patients are breathing adequately, spontaneously and obeying commands.

Post-surgery, patients recovered in the post anesthesia care unit (PACU) before being discharged to the neurosurgical critical care unit.

Data Collection

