Data will be collected from the time of turning off the anesthetic agents till the discharge from recovery room. Patients will be assessed every 5 minutes for the first 30 minutes and every 10 minutes for the next 60 minutes. Data collected will include patient demographics, preoperative neuropsychological assessment data, Age, Intelligence quotient (IQ), Verbal, visual, language memory, education, History of psychiatric illness, Dexterity of the patient and side of surgery, Time of emergence from anesthesia, Vital signs, Glasgow Coma Scale (GCS) score, and Riker agitation score (7-agitated;dangerous agitation, 6-very agitated, 5-agitated, 4-nonagitated;calm and cooperative, 3-sedated but arousable, 2-very sedated, 1-unarousable).

Data Analysis

There are no previous studies looking at the emergence characteristics in patients with temporal lobectomy. As this is an observational study, there are no cause effect relationship to calculate sample size. Emergence characteristics were classified as either smooth emergence (Riker scale 3-4) or agitated emergence (Riker scale >4). Correlation coefficients will be used to compare the data between preoperative neuropsychological scores and the emergence characteristics (smooth vs. agitated) and the time of emergence. Quantitative variables like hemodynamics will be analyzed using student's t-test. Qualitative variables like sex distribution will be analyzed using Chi-square test. A p-value less than 0.05 is considered significant.

CONCLUSION

Smooth emergence (wake up) from anesthesia is an important consideration in patients undergoing neurosurgical procedures as blood pressure changes associated with violent emergence can cause intracranial hemorrhage and brain swelling. At the same time, emergence should also be quick so that patients' neurological function can be assessed at a timely manner. Pattern of emergence from anesthesia is poorly investigated and understood.

REFERENCES

1. Jaakko W. Långsjo, Michael T. Alkire, et al. Returning from Oblivion: Imaging the Neural Core of Consciousness. The Journal of Neuroscience. 2012; 32:4935– 4943
3. Gilliam F. The impact of epilepsy on subjective health status. Curr Neurol Neurosci Rep 2003; 3:357–62

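### Scores are related to emergence only by a marginal correlation, which does not separate a score's contribution from that of the operated side; a secondary side-adjusted estimate would serve the prediction aim

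*Combined protocol and SAP*

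**What the plan says.** The introductory text sets out to "determine if preoperative neuropsychological assessment help predict the pattern of emergence", and Study Objective and Hypothesis repeats the aim as whether "preoperative neuropsychological assessment help predict the quality of emergence". The hypothesis itself is weaker: "there will be a relationship between preoperative neuropsychological assessment scores" (and limbic volumes) and the quality of emergence.

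Background explains why the operated side could matter. It begins "Due to asymmetry of temporal neocortical (dominant vs nondominant) and mesial temporal functional representations", and concludes that losing these structures and their functions "complicates emergence from anesthesia in these patients". Data Collection accordingly lists "Dexterity of the patient and side of surgery".

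Data Analysis then gives the only stated analysis of scores against emergence: "Correlation coefficients will be used to compare the data between preoperative neuropsychological scores and the emergence characteristics (smooth vs. agitated", extended in the same sentence to time of emergence. Student's t-test is planned for quantitative variables and chi-square for qualitative ones, at p<0.05. Side and dexterity do not appear in Data Analysis, and no regression, partial correlation or stratification is named. No sample size is given.

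**The concern.** The operated side is known before surgery, and it is the one factor that the protocol's own rationale picks out. If scores differ between patients having dominant-side and nondominant-side surgery, and emergence does too, a score will correlate with emergence even if it tells the clinician nothing once the side is known. The report could then say that the score predicts emergence when it only marks the side. Conversely, a score that matters on one side only is diluted in a pooled coefficient, and opposing side effects can hide a real within-side association.

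The t-test and chi-square sentences could cover a comparison of side between emergence groups. They do not give a score association with side held fixed.

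**Working it through.** **Stated figure.** There is none to reproduce: the documents give no sample size, power, effect size or event count. Every input below except alpha is an assumption. Alpha is 0.05 from Data Analysis, taken as two-sided.

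**How side enters the correlation.** Let a be the correlation of side with score, b that of side with emergence, and p the score-emergence correlation with side held fixed. Then

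marginal r = p·√((1−a²)(1−b²)) + a·b.

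If a or b is zero, side creates no correlation. If p = 0, the marginal r is a·b. Masking is also possible: p = 0.3, a = 0.5, b = −0.5 gives 0.3 × 0.75 − 0.25 = −0.025.

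**Score with no within-side association, outcome time of emergence.** Take a 50:50 split of sides and a side shift of d within-side SDs in both score and time, in opposite directions. Then |a| = |b| = (d/2)/√(1+d²/4), so |r| = (d²/4)/(1+d²/4). The chance of p<0.05 is approximately Φ(k−1.96) + Φ(−k−1.96), with k = atanh(|r|)·√(N−3). At N=60, √57 = 7.55.

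| d | \|r\| | k | Formula | Simulation, unadjusted | Simulation, adjusted for side |
|---|---|---|---|---|---|
| 0.3 | 0.022 | 0.17 | 5.3% | 5.4% | about 5% |
| 0.5 | 0.059 | 0.44 | 7.3% | 7.2% | about 5% |
| 0.8 | 0.138 | 1.05 | 18.2% | 18.5% | about 5% |
| 1.0 | 0.200 | 1.53 | 33.4% | 34.4% | about 5% |

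The unadjusted simulation gives 5/6/11/19% at N=30 and 6/9/28/53% at N=100 for the same four shifts.

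**Smooth versus agitated, N=60, by simulation.** With a 0.5 SD score shift and 40% vs 25% agitated by side, the unadjusted correlation is significant in 5.2% of studies. With 0.8 SD and 50% vs 20%, it is significant in 15.1%. A penalised logistic model with side gives 4.5% and 4.2%.

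**Association on one side only.** With r = −0.5 on one side and 0 on the other, N=60, the pooled r is about −0.25 with or without adjustment, and power is 49%. On the affected side alone (n=30) power is 83%. With Bonferroni for two sides it is Φ(0.549 × √27 − 2.241) = Φ(0.61) = 73%. With a common r = −0.3 the ordering reverses: 37% per side against 66% pooled. By-side estimates can therefore supplement the pooled result but not replace it.

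**The case against.** The strongest reply is that nothing in the documents asks for value beyond side. The hypothesis is of a relationship, and the correlation is valid for it. A score that tracks emergence partly through side still carries predictive information, and the introductory text is modest: "Hence it is essential to have a clue about post anesthesia emergence behavior". This stands in part. The correlations should be kept, and the rates above describe detection of a true marginal association, not false positives for the stated hypothesis. It does not remove the gap for the prediction aim, because a clinician already knows the side.

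Second, Background says that loss of asymmetrically represented structures complicates emergence. A reader might infer that one side emerges worse, or that scores differ by side. The text says neither, and side-driven correlation needs both. This stands, and is why the size is unknown. At shifts of 0.3 to 0.5 SD the effect nearly vanishes.

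Third, a reader might infer that a correlation can never tell a useless score from a useful one. That is too strong. At N=60, with a 0.8 SD score shift and 50% vs 20% agitated, a score with no within-side effect gives r of about −0.12, significant in about 15% of studies. One with a within-side log-odds of −0.8 per SD gives about −0.40, significant in 91%. The coefficient differs greatly between those cases. It just does not isolate the part due to side.

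Fourth, the remedy has limits. Adjustment does not cure dilution, and the number of estimates grows. Both points stand and shape the fix.

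**Conclusion.** The point holds as a cheap improvement, not as an error in the planned test. The correlation answers the stated hypothesis. For the prediction aim, it leaves a score's contribution mixed with that of the operated side, although the rationale highlights dominance and the variables needed are collected. That no adjustment is planned is inferred from the absence of any covariate, stratum or model in Data Analysis.

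The practical effect ranges from almost nothing (7% against 5% at 0.5 SD shifts) to moderate (about 18% against 5% at 0.8 SD), given N=60, equal sides, and equal shifts in score and time. The documents support none of these inputs, so they illustrate the problem and do not estimate it. They do not support a claim that the plan inflates type I error or that its correlations are uninformative.

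**What to change.** Keep the planned correlations for the hypothesis. Pre-specify beside them, for each score, one secondary model per outcome with dominance of the operated side as the only covariate:

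- smooth versus agitated: logistic regression, penalised if agitated cases are few;
- time of emergence: linear regression on log time.

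State the rule that derives dominance from side and dexterity, and say that it is a proxy. Report estimates with 95% confidence intervals. Show score-emergence estimates by side descriptively, since the adjusted model does not address dilution. Describe a score as adding information beyond side only if the adjusted estimate supports it. AUCs for side alone and for side plus score are optional. How repeated Riker scores become one class is a separate matter, which the planned correlation needs settled in any case.

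**Cost.**

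- *Data and power.* No new data; one degree of freedom per model. At N=60 and a within-side r of −0.3, power falls from 65.6% to 64.9% if side is irrelevant. If side acts only through a 0.8 SD score shift, it falls from 71.8% to 64.7%, about 7 points.
- *Proxy error.* With 10% of dominance misclassified, adjustment brings the rate at 0.8 SD down to 7%, not 5%.
- *Precision.* At N=30 with about 7 agitated cases, the SE of the log odds ratio is about 0.51, so the upper 95% limit is exp(2 × 1.96 × 0.51) ≈ 7.4 times the lower. There is little room for further covariates.
- *Volume.* Counting IQ and verbal, visual and language memory as four scores, with two outcomes, this adds 8 adjusted and 16 by-side estimates without multiplicity control. They should be labelled secondary.

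### The aim is to predict smooth versus agitated emergence, but the scores are linked to that class only by an unnamed correlation coefficient, whose size depends also on the share of agitated patients and so does not quantify prediction.

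*Combined protocol and SAP*

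**What the plan says.** The Study Objective and Hypothesis section sets a predictive aim: "to determine if preoperative neuropsychological assessment help predict the quality of emergence". The opening paragraphs, before Background, state the same aim for the pattern of emergence. The hypothesis is more modest: "there will be a relationship between preoperative neuropsychological assessment scores", together with limbic structure volumes, and the quality of emergence.

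Data Analysis makes the outcome binary: "Emergence characteristics were classified as either smooth emergence (Riker scale 3-4) or agitated emergence (Riker scale >4"). It then links scores to outcome: "Correlation coefficients will be used to compare the data between preoperative neuropsychological scores and the emergence characteristics (smooth vs. agitated"), and applies the same unnamed coefficient to time of emergence.

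Two other tests are listed, each with an example that is not a neuropsychological score: "Quantitative variables like hemodynamics will be analyzed using student's t-test" and "Qualitative variables like sex distribution will be analyzed using Chi-square test". The decision rule is "A p-value less than 0.05 is considered significant". There is no sample size: "As this is an observational study, there are no cause effect relationship to calculate sample size". No expected share of agitated patients is given. The plan contains no odds ratio, regression model, AUC, sensitivity, specificity or cut-off.

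**The concern.** A correlation between a score and a two-level class combines two quantities: how far apart the smooth and agitated groups lie on the score, and how the patients divide between the groups. Only the first bears on how well the score tells an agitated patient from a smooth one. The second describes the case mix of the sample.

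The stated aim concerns prediction, so a reader will want to know how well a score separates the two kinds of patient, or how the odds of agitation change along the score. Followed as written, the plan yields a coefficient and a p-value. The same coefficient can mean modest discrimination in one sample and clearly better discrimination in another, and centres with different agitation rates could not compare coefficients directly. According to Data Analysis there are no earlier studies in this population, so the reader has no outside agitation rate with which to interpret r.

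**Working it through.** The plan states no correlation, effect size, power or sample size, so there is no figure to reproduce. The check asks how the planned statistic behaves.

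**Inputs**
- From Data Analysis: a binary outcome (smooth or agitated), a correlation coefficient of unnamed type, and a significance level of 0.05.
- Assumed, because the documents do not give them: scores normal with equal SD in both groups; a standardised mean difference d of 0.5 to 1.5; a share agitated p of 5% to 50%.

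**Formulas**
- Point-biserial correlation: r = d√(p(1−p)) / √(1 + d²p(1−p)).
- Discrimination: AUC = Φ(d/√2), which does not contain p.

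**Step 1: same separation, different r.** For d = 1, AUC = Φ(0.707) = 0.76. At p = 0.5, r = 0.5/√1.25 = 0.45. At p = 0.1, r = 0.3/√1.09 = 0.29. The full set is:

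| d | AUC | r at 5% | r at 10% | r at 20% | r at 30% | r at 50% |
|---|---|---|---|---|---|---|
| 0.5 | 0.64 | 0.11 | 0.15 | 0.20 | 0.22 | 0.24 |
| 0.8 | 0.71 | 0.17 | 0.23 | 0.31 | 0.34 | 0.37 |
| 1.0 | 0.76 | 0.21 | 0.29 | 0.37 | 0.42 | 0.45 |
| 1.5 | 0.86 | 0.31 | 0.41 | 0.51 | 0.57 | 0.60 |

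Along a row, discrimination is constant and r roughly doubles or more from 5% to 50% agitated. Down a column, r rises with separation. Both influences are real.

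**Step 2: same r, different discrimination.** Inverting the formula gives d = r / (√(1−r²)·√(p(1−p))). For r = 0.30:

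| Share agitated | d | AUC |
|---|---|---|
| 5% | 1.44 | 0.85 |
| 10% | 1.05 | 0.77 |
| 20% | 0.79 | 0.71 |
| 30% | 0.69 | 0.69 |
| 50% | 0.63 | 0.67 |

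**Step 3: does a rank coefficient avoid this?** The type is not named, so rank correlations were simulated at d = 1. At 10%, 20% and 50% agitated, Spearman's coefficient is 0.27, 0.36 and 0.45, and Kendall's is 0.23, 0.30 and 0.37. AUC stays at 0.76. The point therefore holds for all three coefficients.

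**Step 4: what the p-value shows.** The test of a point-biserial r is the two-sample t-test on the scores. In one simulated data set of 32 smooth and 8 agitated patients, both gave p = 0.0036. It is a valid test that the group means differ. It does not measure predictive performance.

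**Step 5: precision of the AUC.** AUC does not move with the share agitated, but its precision does. Take an assumed 40 patients, 4 of them agitated, and AUC A = 0.76. The Hanley–McNeil terms are A/(2−A) = 0.613 and 2A²/(1+A) = 0.656. The variance is [0.76×0.24 + 3×(0.613−0.578) + 35×(0.656−0.578)]/144 ≈ 0.021, so the SE is about 0.145. The lower 95% limit is 0.76 − 1.96×0.145 ≈ 0.48, and the upper limit reaches the bound of 1.

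**The case against.** The strongest defence is that the hypothesis speaks of a relationship, and a correlation with its p-value tests exactly that. This is a first, exploratory study and does not set out to build a prediction model. If r and the number agitated are both reported, a reader who accepts the normal model can work back to an AUC. All of this stands. A reader might infer that the study cannot address its question at all. The documents do not support that, because the test of association is sound. What is missing is a measure of how well a score predicts, which the aim calls for and the plan does not provide. The plan also does not say that the number agitated will be reported beside r.

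Three other strong readings are tempting and should not be drawn.

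- **That the agitated share alone fixes r.** It does not. At 20% agitated, r runs from 0.20 to 0.51 as d goes from 0.5 to 1.5.
- **That r can never approach 1.** In the two-group model used here, r tends to 1 as separation grows. At p = 0.5 and d = 5 it is 2.5/√7.25 = 0.93. A ceiling near 0.80 arises only when a single normal variable is cut at its median, which is a different model.
- **That a few slow wakers would dominate the analysis of time of emergence.** The plan does not name the coefficient, so a rank correlation is not excluded, and the documents give no distribution of times. The unarousable patients in the opening paragraphs describe a level of sedation and say nothing about the spread of emergence times.

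It is also fair to say that the AUC does not cure a shortage of agitated patients. With 4 in 40, the interval in step 5 would be nearly uninformative.

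**Conclusion.** The point holds, as a mismatch between the predictive aim and the reported statistic. The planned coefficient tests the hypothesised relationship but does not quantify prediction. For a fixed AUC of 0.76, r ranges from 0.21 to 0.45 as the share agitated goes from 5% to 50%. For a fixed r of 0.30, AUC ranges from 0.85 to 0.67 over the same shares.

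These figures rest on normal scores with equal SD and on assumed values of d and p, because the documents supply neither. The direction of the effect does not depend on the particular values chosen, and the simulated rank coefficients show it too. The study remains usable as it stands. This is a change that should be made, since it supplies the answer the aim asks for from data already being collected.

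**What to change.** In Data Analysis, state that for each neuropsychological score the report will give:

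1. the AUC for agitated versus smooth emergence with a 95% confidence interval (DeLong or bootstrap);
2. the odds ratio per 1 SD of score from logistic regression with a 95% confidence interval, using Firth's penalty if few patients are agitated;
3. the number of agitated patients and the number of smooth patients.

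The correlation with the class may stay as a descriptive figure, with its type named.

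The cost is a change of wording and a few more lines of output; no new data are needed. The drawback is that the intervals will be wide if few patients are agitated, and the report should say so.

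As a side note only: name the coefficient for time of emergence as well. Spearman's is a reasonable choice if the times prove skewed.

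### Several neuropsychological scores are tested against two emergence outcomes at an unadjusted 0.05, with no primary association, multiplicity rule or exploratory label

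*Combined protocol and SAP*

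**What the plan says.** The aim, under Study Objective and Hypothesis, is "to determine if preoperative neuropsychological assessment help predict the quality of emergence". The hypothesis is that "there will be a relationship between preoperative neuropsychological assessment scores and the limbic structure (hippocampus, amygdala and thalamus) volumes with the quality of emergence". Both name one outcome, quality of emergence, but neither singles out a score.

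Data Collection lists the assessment items as "Intelligence quotient (IQ), Verbal, visual, language memory", within a broader and open list of preoperative data.

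Data Analysis splits emergence into smooth (Riker 3–4) and agitated (Riker above 4). It then plans correlation coefficients between "preoperative neuropsychological scores and the emergence characteristics (smooth vs. agitated) and the time of emergence", so time of emergence enters as a second outcome. The only decision rule is "A p-value less than 0.05 is considered significant". The same section says "There are no previous studies looking at the emergence characteristics in patients with temporal lobectomy" and gives no sample size.

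On vital signs, Data Collection states: "Patients will be assessed every 5 minutes for the first 30 minutes and every 10 minutes for the next 60 minutes". Data Analysis adds: "Quantitative variables like hemodynamics will be analyzed using student's t-test".

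**The concern.** The study asks whether preoperative assessment predicts emergence. The plan answers with a set of tests, each declared significant at 0.05 on its own. Nothing says which test carries the answer, and nothing controls the error over the set. If no score were related to emergence, following the plan exactly would still produce at least one significant predictor far more often than 1 time in 20. Readers could take that result as evidence that the score helps foresee a difficult wake-up.

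A smaller issue of the same kind affects the vital signs. Each patient contributes repeated readings, a t-test needs one independent value per patient, and the plan does not say how the readings become one value.

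**Working it through.** The plan states no family-wise error, sample size or power, so there is no figure of its own to reproduce.

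**Inputs from the documents.** Significance level 0.05 per test (two-sided assumed); two outcomes; readings every 5 minutes for 30 minutes, then every 10 minutes for 60 minutes.

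**Assumed inputs.** Four scores (IQ, and verbal, visual and language memory); n = 40; 25% agitated; correlation between scores 0.3 to 0.7; outcomes uncorrelated or correlated 0.5.

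**Number of tests.**
- Quality of emergence only: 4 × 1 = 4.
- Both outcomes: 4 × 2 = 8.

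**Chance of at least one false positive, independent tests:** 1 − 0.95^m.
- m = 4: 1 − 0.95^4 = 0.185, about 19%.
- m = 8: 1 − 0.95^8 = 0.337, about 34%. The expected number of false positives is 8 × 0.05 = 0.4.

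**Correlated tests.** Scores from one battery are usually correlated, which lowers these figures. Simulation under no association, with point-biserial tests for emergence class and Pearson tests for time, gave the following as score correlation goes from 0.7 to 0.3:
- 4 tests: about 12–17%.
- 8 tests: about 24–32%.

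**Sensitivity to the number of scores.** Over both outcomes with independent tests, 3 scores give 1 − 0.95^6 = 26% and 6 scores give 1 − 0.95^12 = 46%.

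**Effect of control.** One named association has a 5% error. Bonferroni over 8 tests uses 0.05/8 = 0.00625 per test and gave a simulated family-wise error of about 4–5%.

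**Power cost.** The proposed primary outcome is binary. With n = 40, an underlying correlation of 0.4 and 25% agitated, simulated power is about 46% at 0.05 and about 18% at 0.00625. Holm over four scores starts at 0.05/4 = 0.0125, so its first-step power lies between these two values.

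**Vital signs.** The schedule gives 30/5 + 60/10 = 12 readings, fewer if the patient leaves recovery early. If all 12 were pooled as independent with a constant within-patient correlation ρ, the variance would be understated by a factor of 1 + 11ρ.
- ρ = 0.3: factor 4.3. The nominal cut-off 1.96 becomes 1.96/√4.3 = 0.945, giving a true type I error of about 34%.
- ρ = 0.7: factor 8.7. The cut-off becomes 1.96/√8.7 = 0.664, giving about 51%.

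If correlation fades quickly with time, the error can be as low as about 10%. With one 30-minute mean or peak per patient, simulated error was 4.6–5.4%.

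**The case against.** The strongest reply is that this is a first, observational, descriptive study with no prior data. Whether such a study must name a primary association or adjust is partly a matter of taste, and one sentence calling the results exploratory would answer most of the point. That stands as regards the remedy, and it is why an exploratory label is an acceptable fix. It does not remove the problem, because the plan contains no such label and does contain a blanket significance rule.

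A second reply is that the aim and hypothesis already point to quality of emergence. This also stands. It makes the 4-test figure the one that matches the study's question; 34% applies to everything the plan tests. But no score is singled out, and time of emergence is tested on the same footing.

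Several stronger readings are tempting but not supported:
- A reader might add the three limbic volumes in the hypothesis and count 11 or more tests. Data Analysis gives no analysis for them, so those tests are not in the plan.
- A reader might infer selective reporting. The documents plan all scores against both outcomes and do not suggest that only some would be reported.
- A reader might conclude that the hemodynamic t-test is invalid. That follows only if readings are pooled as independent, which the plan does not say. With one summary per patient the test is sound.
- A reader might cost the fix at 73% versus 43% power (n = 40, correlation 0.4). Those figures treat emergence as continuous, whereas the plan makes it binary.

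**Conclusion.** The point holds and should be addressed, though it does not prevent the study from being run. As written, the plan can declare a significant predictor by chance with probability up to 19% for its stated question and up to 34% over everything it tests. The more realistic figures are about 12–17% and 24–32%. All four rest on an assumed four scores; the last two also rest on n = 40, 25% agitated and score correlations of 0.7 to 0.3. A different number of scores would change the size but not the conclusion.

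Naming a primary score is not enough by itself. Repeated Riker readings are not reduced to one emergence class per patient, and Riker 1–2 falls in neither class. Until both are settled, the primary outcome is itself open to choice after the data are seen.

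The hemodynamic gap is minor: it lies outside the aim and hypothesis, and its effect depends on a choice the plan leaves unstated.

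**What to change.** Amend Data Analysis as follows:

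1. Make quality of emergence (smooth versus agitated) the primary outcome. State in advance which Riker reading or summary gives each patient a single class, and how Riker 1–2 is handled.
2. List the scores to be tested. Either name one as primary at 0.05, or apply Holm across the listed scores for this outcome.
3. Report time of emergence and all other associations as exploratory, with estimates and 95% confidence intervals.
4. If no score can be justified beforehand and no correction is wanted, label every association exploratory and remove the blanket significance rule.
5. For hemodynamics, compare one pre-named summary per patient over a fixed window (for example the mean over the first 30 minutes), or fit a mixed model with a patient effect. Report the result as exploratory.

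This takes a few sentences and no new data. The associations outside the primary analysis will carry less weight, and a single vital-sign summary loses the time pattern unless the mixed model is used. Correction also costs power, from about 46% at 0.05 to about 18% under the strictest option, Bonferroni over 8 tests, on the assumptions above. That favors one justified primary score, or Holm over the few scores for one outcome, over a correction across all 8 tests.
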